Pre-Analysis Plan

Increasing the Efficacy and Diffusion of COVID-19 Messaging for Vaccination

This Draft: January 24, 2022

1. Introduction

This study will distribute videos of health care professionals encouraging Covid-19 vaccination to a large sample of Facebook and Instagram users, and will test the most effective ways to maximize diffusion of this vaccine-related content to increase vaccination rates. The study sample will be U.S. states where vaccination rates remained low in fall 2021. The experimental design is an RCT with 4 groups, randomized at the county level: 1) a control group which receives no intervention, 2) a treatment group in which Facebook users receive ads which include videos of health care professionals telling them to get vaccinated, 3) a treatment group in which Facebook users receive ads which include videos of health care professionals encouraging them to help their friends to get vaccinated, and 4) a treatment group in which Facebook users receive ads which include videos of health care professionals encouraging them to get their most influential friends to help their friends get vaccinated. The study team has built a website to host the videos of health care professionals which answer common questions about Covid-19 vaccination. The primary outcome of interest is Covid-19 vaccination rates. The investigators will also measure engagement with vaccine-related content in each treatment group. Secondary outcomes which may be considered include Covid-19 case and symptoms prevalence, Covid-19 hospitalization or mortality, and outcomes related to movement, travel, and closures.

2. Sample and Treatment

2.1 Sample Population

The experimental sample includes all states where less than 60% of the total population had received a first dose of Covid-19 vaccine by October 21, 2021. There are 1402 counties in the 19 states satisfying those criteria (Alabama, Alaska, Arkansas, Georgia, Idaho, Iowa, Indiana, Louisiana, Michigan, Mississippi, Missouri, Montana, North Dakota, Ohio, Oklahoma, South Carolina, Tennessee, West Virginia, Wyoming). Excluding the five counties with missing data, there are 1,397 counties in the experiment, of which there are 468 counties in the control group, 310 counties in T1 ("direct" messaging) treatment, 309 counties in T2 ("friends" messaging), and 310 counties in T3 ("gossips" messaging).

2.2 Treatments

The treatments are all initiated through Facebook platforms. Facebook users located in treatment counties will be exposed to one of three ad campaigns featuring a set of videos about Covid-19 vaccination. The videos feature doctors and nurses from Massachusetts General Hospital (MGH), Harvard Kennedy School (HKS), Johns Hopkins School of Nursing, Harvard Medical School, Lynn Community Health Center, St. Anthony North Family Medicine, and McGovern Medical School. In the videos, doctors and nurses are usually wearing scrubs or other medical uniforms. The ad videos were filmed by doctors and nurses using their phones, and edited by professionals at Code3. The videos are short (approximately 30 seconds in length).

All of the ads are associated with the project Facebook page titled "The Doctors for Coronavirus Prevention Project." Users see the ads and name of the Facebook group associated with the ads on their Facebook feeds. Some ads are also served on Instagram. Watching the videos is completely optional for Facebook users. The ads are all targeted to Facebook users aged 18 and older. The ad campaign is programmed to optimize for the Facebook "reach" objective, with budget allocations roughly proportional to population.

Treatment 1: "Direct" messaging: Facebook users receive ads with a video of a doctor or nurse answering a common question or addressing a common myth about the Covid-19 vaccine.

Treatment 2: "Friends" messaging: Facebook users receive ads which encourage them to help their friends to get vaccinated.

Treatment 3: "Gossips" messaging: Facebook users receive ads which encourage them to ask their most influential friends to help their friends to get vaccinated.

In treatments 3 and 4, participants will have the option to sign up to be a "vaccine ambassador," in which case they will get notifications when the study team posts new vaccine-related content, and will receive reminders about encouraging their friends to be vaccinated.

2.3 Sample Frame

We began to roll out the campaigns on December 22, 2021. We plan to run the Facebook campaigns for five weeks (until January 27, 2022).

2.4 Study website

The Facebook ads for all treatment groups link to a website built for the study:

<https://www.doctorsforcovidprevention.org>. Treatment 1 participants are directed to a page of video thumbnails with all of the videos recorded by doctors and nurses which answer questions and address myths about the Covid-19 vaccine. Treatments 2 and 3 participants are directed to a website which includes these same videos, and also encourages website visitors to share the vaccine-related content with their friends. The website for treatments 2 and 3 also allows visitors to sign up to be a "vaccine ambassador." Interested website visitors can enroll formally as vaccine ambassadors through our site. They can share their contact information with the study to a) be entered into prize lotteries, b) receive reminders to share content with others, c) be contacted in the future for possible follow-up surveys. These individuals are asked to give their informed consent at this time and are screened based on whether they live in a treated county and whether they are 18 years or older.

The display of doctor/nurse videos on the study website is randomized in two ways. First, website visitors are randomized into two possible video framings: the “myth” site or the “question” site. In the “myth” version, doctors/nurses respond to common myths about the Covid-19 vaccine (e.g. the Covid-19 vaccine can give me Covid), while in the “question” version, the doctors/nurses respond to a question (e.g. can the Covid-19 vaccine give me Covid?). Second, the order that videos are shown is randomized. For the page which only shows video thumbnails, this means the order of the thumbnails is random for each unique website visitor. For the page which encourages people to share vaccine-related content, the random ordering of videos means that the “featured” video is randomized between unique website visitors.

2.5 Treatment Assignment

The counties in the study sample were randomized into three treatment groups and a control group: 1) a “direct” messaging group (T1), 2) a “friends” messaging group (T2), 3) a “gossips” messaging group (T3), and 4) a control group which did not receive any Facebook ads from us.

Randomization was conducted at the county level. County-level randomization was stratified by three characteristics: 1) state, 2) political leaning (according to 2020 election results), and 3) baseline vaccination rates. For political leaning, counties were divided into below- and above- median GOP vote in the 2020 presidential election. For baseline vaccination rates, counties were divided into above- and below-median percentage of the population that had received the 1st dose of Covid-19 vaccine.

After stratifying on these three variables, strata were adjusted so that no stratum was smaller than 9 counties. Strata with fewer than nine counties were dissolved by baseline percentage of population with first dose of vaccine. For the three states (South Carolina, Michigan, and Wyoming) where this does not result in strata that have at least nine counties, we dissolve instead by baseline GOP vote share. In total, this left us with 47 strata.

Exceptions: County-level GOP votes were not available for Alaska, and so this stratification variable was used for the other 18 states in the sample only.

Out of the 1,397 counties which fit the eligibility criteria for the experiment, we assigned 468 counties to the control group, 310 counties to T1 (“direct” messaging) treatment, 309 counties to T2 (“friends” messaging), and 310 counties to T3 (“gossips” messaging).

3. Hypotheses

Primary hypotheses:

1. Do the ads affect the new Covid-19 vaccinations in treated areas?
 - 1st dose of vaccine
 - 2nd dose/completed vaccination
 - Booster shots
2. Which type of messaging (“direct,” “friends,” or “gossips”) is most effective at driving engagement and shares of vaccine-related content, as well as new vaccinations?

3. Is myth- or question-based messaging more effective at eliciting engagement with vaccine-related content?

Secondary hypotheses:

4. Do the ads affect Covid-19 cases, hospitalizations, or symptoms in treated areas?
5. Do the ads spill over onto other areas that are connected to the treatment counties?
 - Behavioral spillovers: new vaccinations
 - Covid-19 case, hospitalization, symptom impacts
 - Are spillovers more pronounced on the mobility network or the Facebook friendship network?

4. Empirical Analysis

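### Contrasts of Direct with Friends or Gossips compare whole arms (ad, landing page and ambassador offer), so they answer hypothesis 2 only at that level and cannot be credited to the message alone

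*Combined protocol and SAP*

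**What the plan says.** Primary hypothesis 2 (Section 3) asks which type of messaging, direct, friends or gossips, "is most effective at driving engagement and shares of vaccine-related content, as well as new vaccinations". The Introduction adds: "The investigators will also measure engagement with vaccine-related content in each treatment group". Section 4.2 lists engagement (website views, video views, shares) as a secondary outcome, reported by county or by treatment group.

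Section 2.2 distinguishes the three treatments by what the ads say. Section 2.4 then describes where the ads lead:

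- All arms: "The Facebook ads for all treatment groups link to a website built for the study".
- Direct: "Treatment 1 participants are directed to a page of video thumbnails".
- Friends and Gossips: a site with the same videos that "also encourages website visitors to share the vaccine-related content with their friends". It has a featured video and an ambassador sign-up. Those who enrol can enter prize lotteries and "receive reminders to share content with others". Section 2.2 says of ambassadors that "they will get notifications when the study team posts new vaccine-related content, and will receive reminders about encouraging their friends to be vaccinated".

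Only the myth or question framing and the video order are randomized on the site. The type of page is fixed by arm.

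The main model in Section 4.4 is headed as covering content engagement. It has time effects, county effects, one indicator per arm and a baseline value of the outcome. Section 4.7 specifies heteroskedasticity-robust standard errors for core analyses, plus further robustness checks taken from the appendix of another paper.

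A side point: Section 2.2 gives the ambassador option to treatments 3 and 4, and Section 2.4 gives it to treatments 2 and 3. The Introduction counts the control group as group 1, so this is probably a numbering difference, but the two sections should be reconciled.

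**The concern.** Direct differs from the other two arms in ad message, page layout, sharing prompt and ambassador offer, all at once. The page itself prompts sharing, which is one of the outcomes being compared. A report that friends or gossips messaging makes people share more than direct messaging could therefore describe the effect of the page and the reminders, wholly or in part. A programme that reused the ad wording without that page might not get the reported gain. The plan nowhere says that type of messaging means the whole arm.

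A second, smaller issue concerns the model. County effects and a baseline term presuppose informative data from before the campaign, and a website created for the study has none.

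**Working it through.** **Which contrasts are identified.** Give each treated arm a value for four parameters: intercept, Friends message, Gossips message, and sharing/ambassador page (Sections 2.2 and 2.4).

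| Arm | Intercept | Friends message | Gossips message | Page |
|---|---|---|---|---|
| Direct | 1 | 0 | 0 | 0 |
| Friends | 1 | 1 | 0 | 1 |
| Gossips | 1 | 0 | 1 | 1 |

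The rank is 3 for 4 parameters. Subtracting rows:

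- Friends − Direct = Friends message + page
- Gossips − Direct = Gossips message + page
- Gossips − Friends = Gossips message − Friends message

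The first two sums can be estimated, but their parts cannot. The third is free of the page, because both arms use the same site. More counties or more covariates do not change this.

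**What that means for a result.** Write the Friends/Direct ratio of on-site shares as R = m × r, where m is the message effect and r the page and ambassador effect. Then m = R/r. The documents give no value for r, so a range is assumed. For an observed R = 1.5:

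| Assumed r | Implied m |
|---|---|
| 1 | 1.5/1 = 1.50 |
| 1.25 | 1.5/1.25 = 1.20 |
| 1.5 | 1.5/1.5 = 1.00 |
| 2 | 1.5/2 = 0.75 |

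The direction reverses only if r exceeds 1.5. The documents do not say whether the Direct page has share buttons. If it has none, no finite r applies and the on-site share gap is set by design.

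**The Section 4.4 model for website engagement.** There are 310 + 309 + 310 = 929 treated counties; with 468 controls, 1,397. The campaign runs five weeks (Section 2.3).

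1. *Campaign weeks only.* Each arm indicator is constant within a county, so after county and week effects are removed it is zero everywhere (rank 0, with 929 or 1,397 counties). The arm effects cannot be estimated.
2. *With pre-campaign rows of zeros added.* The rank becomes 2 in the 929 treated counties, enough for all between-arm contrasts, and 3 with controls. The estimates equal the raw differences in campaign means, so the added rows bring no information.
3. *Error bars in case 2.* Let T0 be the number of zero rows, T1 = 5 and T = T0 + T1. If a county's weekly values are perfectly correlated, the unclustered robust variance divided by the correct variance is (T0² − T0·T1 + T1²)/(T0·T1·T).
   - T0 = 1: (1 − 5 + 25)/(1·5·6) = 0.70, so a nominal 5% test rejects in 2·P(Z > 1.96·√0.70) = 10%. With the usual degrees-of-freedom factor 6/5 it rejects in 7%.
   - T0 = 5: 25/(5·5·10) = 0.10, giving 54%. With the factor 10/9 it gives 51%.

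   Null simulations over a range of assumed settings (600 trials each) rejected in about 3–8% with one zero week and 17–55% with five. The answer depends on how many empty rows are added and on the within-county correlation. The plan states neither.
4. *One total per county.* In null simulations the Friends–Direct test rejected in 4.1% to 5.8% (18 assumed settings, 3,000 trials each).

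**What pre-landing measures can detect.** For a ratio q and between-county coefficient of variation CV (assumed), solve (q − 1)/√(CV²/310 + (CV·q)²/309) = 1.96 + 0.84 for 80% power. This gives q = 1.26, 1.60 and 2.12 at CV 1, 2 and 3.

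**The case against.** The plan uses direct, friends and gossips as names of arms, places the ambassador option under the treatments, and discloses each arm's page. On that reading hypothesis 2 compares whole arms and can be answered as planned. For a study that wants to maximize diffusion, that is a useful question. This stands. A reader might infer that the page difference biases the engagement contrasts or leaves hypothesis 2 unanswerable; the documents do not support that, because counties were randomized to the whole arm. What remains is that Section 2.2 separates the message types mainly by ad content, and no sentence warns against crediting the result to the wording.

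A reader might also exempt vaccinations. That would be inconsistent: the same arms carry the same bundle, so Direct-versus-Friends or Direct-versus-Gossips vaccination effects are whole-arm effects as well.

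Analysis 1(d) is framed as a comparison of treatment groups and makes no message-only claim. It needs careful interpretation, not correction.

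On the model, the plan does not restrict the rows to campaign weeks, so it would go too far to say that the arm effects can never be estimated. A further figure is tempting: if strata replaced county effects but weekly rows stayed unclustered, a 5% test would reject in 17% to 38% at within-county correlations of 0.25 to 1. The plan does not specify that model, so this is no error rate of the plan. Section 4.7 also promises robustness checks from an appendix that is not available here; whether they include clustering is unknown.

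Finally, clicks and arrivals do not measure sharing, which hypothesis 2 asks about. That is a real limit of the remedy.

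**Conclusion.** The point holds as a limit on interpretation, with a related weakness in the engagement model. Friends–Direct and Gossips–Direct are sound randomized comparisons of whole arms, for on-site engagement and for vaccinations. Neither isolates the message. Gossips–Friends and measures taken before the landing page are not affected by the page difference.

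The identification result rests only on the arm descriptions in Sections 2.2 and 2.4 and on additive message and page effects. If effects are not additive, Gossips–Friends still compares messages, given the shared site. The size of any misattribution is unknown: the 1.50-to-0.75 range, the CVs and the rejection rates rest on assumed inputs and are illustrations.

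For website engagement, the Section 4.4 model is either not estimable or depends on uninformative zero rows, with error bars that vary with how many are added. The change is worth making because a primary hypothesis is involved. It is not critical: engagement is listed as a secondary outcome, and the vaccination analysis can stay as it is.

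**What to change.** 1. **Interpretation.** State in Section 3 that any contrast with Direct, for engagement or vaccinations, estimates the whole arm: ad, page and ambassador offer. Base message-only claims on Gossips versus Friends and, where Direct is involved, on measures taken before the landing page: ad video views, ad clicks if available, and ad-driven first arrivals. Say that these do not measure sharing. Do not count ad shares as purely pre-landing, because a user may share after visiting the site or getting a reminder. Describe 1(d) as a group comparison.
2. **Website engagement model.** Replace the county effects and baseline term with one total per county over the period in which county can be identified, randomization-stratum effects and robust errors. Prespecify Friends–Direct, Gossips–Direct and Gossips–Friends in the 929 treated counties. Keep control-county visits and sharing chains for the spillover analysis.

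The cost is plan wording and one regression; ads, site and randomization stay as they are. The claim about Direct and website sharing narrows to a package effect, and the design cannot show whether wording alone makes arrivals share more. County-level website data cover only part of the campaign (Section 4.3). If ad metrics come only by treatment group, which Section 4.2 allows, county-based inference on them is not possible.

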4.1 Primary Outcomes

1. **Covid-19 vaccinations:** this includes 1st doses, 2nd doses/completed vaccination, and booster shots when available. These data are available at the county level.

4.2 Secondary Outcomes

1. **Engagement with content related to Covid-19:** this includes website views, video views, and social media shares of vaccine-related videos and messaging, disaggregated at the county or treatment group level.
2. **Other Covid-19 outcomes:** depending on data availability, this will include Covid-19 symptoms, cases, hospitalizations, and deaths. The investigators do not expect the study to be well-powered on this outcome.
3. **Other survey outcomes:** if available, we may assess outcomes on vaccine hesitancy according to surveys. The investigators do not expect the study to be well-powered on this outcome.
4. **Other behavioral outcomes:** we may also study whether the treatments have an effect on movement and travel, as well as school or other institutional closures. The investigators do not expect the study to be well-powered on this outcome.

4.3 Website data

The study website collects detailed information on visitors, including the following:

1. County of origin (according to the Facebook ad which referred them to the website) – for part of the experimental timeframe
2. IP Address – for part of the experimental timeframe

3. Version of the website that the user saw
4. Any actions taken on the website along with timestamps (e.g. page view, video views, video shares, message shares, vaccine ambassador sign ups)
5. Sharing chains (e.g. if someone visits the website after it is shared with them from County A, we can follow whether they viewed the website due to a share from someone in County B)

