4.4 Regression Analysis

1. Effects of treatment on county-level outcomes (Covid-19 vaccinations, content engagement, other behavioral or survey outcomes):

- (a) Main analysis: $Y_{ct} = \alpha_t + \gamma_c + \beta_1 Direct_{ct} + \beta_2 Friends_{ct} + \beta_3 Gossips_{ct} + \delta Y_{c0} + \epsilon_{ct}$
 - Y_{c0} is a baseline measure of the outcome
 - *Direct, Friends* and *Gossips* are the three treatment groups. Treatment is assigned at the county level. We may also pool together friends and gossips, or all three treatment groups in some specifications.
- (b) Heterogeneous effects of treatment: $Y_{ct} = \alpha_t + \gamma_c + \beta_1 X_{ct} + \beta_2 Treat_{ct} + \beta_3 Treat_{ct}X_{ct} + \epsilon_{ct}$
 - We plan to explore heterogeneity along the following dimensions:
 - Political leaning (red/blue) – this was a stratification variable
 - Baseline vaccination rates – we stratified on baseline population percentage with 1st dose of vaccine
 - Percentage white/non-white
 - Relevant vaccine mandates
 - Prior/baseline infection rates
 - Urban vs rural

We may look at heterogeneity in specifications which consider each treatment group separately, as well as specifications which pool together treatment groups.

- (c) Distributional impacts using quantile regression
 - We may repeat the exercises above with quantile regressions.
- (d) Do people who visit the study website from different treatment groups click on different content (e.g. vaccine-related videos)? For example, do website visitors respond to myth vs fact videos differentially by treatment group?

2. Comparing the efficacy of myth- vs question-based messaging

- (a) $Y_{ict} = \alpha_t + \gamma_c + \beta \mathbb{1}(Myth_{ict}) + \epsilon_{ict}$
 - Y_{ict} stands for engagement-related outcomes such as video views, website visits, and video shares
 - We will examine myth- vs question-based messaging at both the Facebook ad level and at the website level. (The videos vary in whether they are myth- or question-based both in the Facebook ads which are served to users, as well as in the videos which are visible to website visitors.)

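### The website-level myth versus question model needs each visitor's county, which is recorded for only part of the campaign and is not needed for that contrast

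*Combined protocol and SAP*

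**What the plan says.** Section 4.4, item 2(a), gives one equation for myth versus question messaging: "Y_{ict} = \alpha_t + \gamma_c + \beta \mathbb{1}(Myth_{ict}) + \epsilon_{ict". The subscripts are visitor, county and time, and γ_c is a county effect. The outcomes are engagement measures such as video views, visits and shares. The same equation is to be used at the Facebook ad level and at the website level.

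Section 2.4 describes the website assignment: "website visitors are randomized into two possible video framings". It mentions no stratification by county.

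Section 4.3 lists what the site records:
- location from the referring ad: "County of origin (according to the Facebook ad which referred them to the website", available "for part of the experimental timeframe";
- "IP Address – for part of the experimental timeframe";
- "Version of the website that the user saw", with no time limit stated;
- timestamped actions and sharing chains, also with no time limit stated.

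Section 3 lists the comparison as hypothesis 3, under the primary hypotheses. Section 4.2 classes engagement as a secondary outcome. Section 4.6 applies controls selected by machine learning to all regressions, with county-level candidates among them.

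**The concern.** The equation asks for a variable that the plan itself describes as incomplete. The randomised exposure (site version) and the outcomes (actions) carry no such restriction. Standard fixed-effects software drops a record whose group identifier is missing. Unless something else is specified, visitors who were randomised and observed would therefore leave the analysis for lack of a covariate that the randomisation does not require.

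Two things are at stake. One is precision for a question listed among the primary hypotheses. The other is coverage: the estimate would describe only the recorded part of a campaign that runs from 22 December 2021 to 27 January 2022 (36 days). In addition, because no rule is written for a missing county, the analysis sample could be settled after the data are seen.

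**Working it through.** The plan gives no visitor count, power, effect size or recorded share for this comparison, so there is no planned figure to reproduce.

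**1. Is county needed for validity at the website level?** Framing is assigned to the visitor, and no allocation by county is described. A visitor's county is therefore independent of framing by design, and a simple contrast by site version is unbiased. County effects can change only the precision.

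**2. Cost of keeping only visitors with a county.** Let f be the share of visitors with a recorded county (assumed range).
- SE ratio = 1/sqrt(f).
- If the full sample had 80% power at two-sided 5% (also assumed), restricted power = Φ(sqrt(f) × (1.960 + 0.842) − 1.960).

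| f | SE ratio | Power instead of 80% |
|---|---|---|
| 0.90 | 1.05 | 76% |
| 0.75 | 1.15 | 68% |
| 0.50 | 1.41 | 51% |
| 0.25 | 2.00 | 29% |

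**3. Simulation.** The number of treated counties, 310 + 309 + 310 = 929, is from section 2.1. The remaining inputs are assumptions: 10,000 visitors, counties of unequal size, between-county SD 5 points, base rate 20%, true myth effect 2 points, 10% of visitors arriving by share (with a rate 5 points higher), and county known for half the period and for no share arrivals. There were 1,500 runs.

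| Analysis | Mean estimate (truth 0.0200) | Empirical SD |
|---|---|---|
| All visitors, no county effects | 0.0200 | 0.0083 |
| Visitors with a county, no county effects | 0.0204 | 0.0120 |
| Visitors with a county, with county effects | 0.0202 | 0.0132 |
| All visitors, unknown-county category | 0.0199 | 0.0086 |

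All four are unbiased to within simulation error. The restricted county-effects model has 0.0132/0.0083 = 1.6 times the SD of the all-visitor contrast. Most of this comes from the lost visitors: the recorded share is 0.5 × 0.9 = 0.45, and 1/sqrt(0.45) = 1.49. The rest comes from fitting many county effects to few visitors (0.0132/0.0120 = 1.10).

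**4. What the simulation does not test.** It gives every visitor, including share arrivals, an independent framing draw, and it holds the effect constant over time. It therefore says nothing about framing inherited through a shared link, or about a myth effect that differs between the recorded and unrecorded periods.

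**The case against.** The strongest reply is that the plan never states a complete-case rule. A category for unknown county would keep γ_c and every visitor, and in the simulation it recovers nearly all the precision (SD 0.0086 against 0.0083). IP address might also supply location if its period differs from that of the county field. This stands as far as it goes: deletion is what a literal fit would do, not what the plan says it will do. But the plan mentions no unknown-county category and does not say whether the two recording periods overlap.

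A reader might go further than the documents allow in three ways.
- **That share arrivals are lost.** They have no referring ad of their own, but section 4.3 says sharing chains are followed with reference to counties. A county may be assignable to them; the plan does not say whether it would serve as γ_c.
- **That pooling every visitor is safe.** Section 2.4 does not say whether a shared link carries the sharer's framing or triggers a new draw. Sharing is itself an outcome of the model. If framing is inherited, share arrivals are not independently randomised, and they are clustered by sharer.
- **That county effects are superfluous throughout.** The argument from visitor-level randomisation covers the website only. The plan does not describe how myth and question ads are allocated among Facebook users, so county effects may matter at the ad level.

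It can also be said that removing γ_c alone may not be enough. County-level controls selected under section 4.6 would bring the county requirement back. That is correct, and the remedy has to cover it.

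**Conclusion.** The point holds for the website-level comparison. As written, the model depends on a partly recorded variable that the randomised contrast does not need. A standard fit would lose precision and coverage of the campaign period, with no gain in internal validity. The evidence does not point to bias from the restriction.

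The size cannot be fixed, because the plan gives neither the recorded share nor the number of visitors. Over an assumed share of 0.90 down to 0.25, the standard error rises by a factor of 1.05 to 2.00. These figures assume that visitors without a county are dropped and are otherwise similar in outcome variance. Loss of share arrivals remains a possibility only, and nothing here bears on the ad-level model.

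**What to change.** In section 4.4, item 2(a), separate the website-level comparison from the ad-level one and leave the ad-level model unchanged. For the website level:

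1. Make the primary analysis all ad-referred visitors, compared by randomised site version, with time effects and an indicator for landing page (T1 page or T2/T3 page). Omit γ_c and any selected control that needs a county, or keep them with an explicit unknown-county category.
2. State whether a visitor arriving by a shared link receives a fresh framing draw. If so, include these visitors. If not, analyse them separately or cluster by sharing chain.
3. Keep the county-effects model, on visitors with a recorded county, as a sensitivity analysis.
4. Report the number of visitors without a county by framing, and the dates over which county and IP address were recorded.

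The cost is one changed equation, a few sentences, and a check of how the site handles shared links. No new data are needed, provided that the site-version and sharing-chain records run for the whole campaign, as section 4.3 implies, and that the version record identifies the landing page.
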